11.4.8.2 Pregnancy

Subjects will be counseled to inform the investigator of any pregnancy that occurs during study treatment and for 90 days after the last dose of study drug.

If a subject or the female partner of a male subject becomes pregnant while participating in the study, study drug will be permanently discontinued immediately. The investigator will notify the medical monitor and Vertex Global Patient Safety (GPS) within 24 hours of the site's knowledge of the subject's (or partner's) pregnancy using the Pregnancy Information Collection Form.

The subject or partner will be followed until the end of the pregnancy and the infant will be followed for 1 year after the birth, provided informed consent is obtained. A separate ICF will be provided to explain these follow-up activities. Pregnancy itself does not constitute an AE.

12 STATISTICAL AND ANALYTICAL PLANS

12.1 Sample Size and Power

This open-label rollover study will enroll subjects from Study 113B and Study 115. No formal sample size calculations have been performed. Approximately 56 subjects from Study 113B and approximately 65 subjects from Study 115 are potentially eligible for enrollment.

12.2 Analysis Sets

12.2.1 All Subjects Set

The All Subjects Set will be defined as all subjects who are enrolled in Study 116 or received at least 1 dose of TEZ/IVA in Study 116. This analysis set will be used for all individual subject data listings and the disposition summary table, unless specified otherwise.

12.2.2 Full Analysis Set

The Full Analysis Set (FAS) will be defined as all subjects who are enrolled in Study 116, who received at least 1 dose of TEZ/IVA in Study 116, and have an eligible genotype. The FAS will be used for efficacy analyses, unless otherwise specified.

The 115 FAS will be defined as the subset of FAS who were enrolled in parent Study 115. The 113B FAS will be defined as the subset of FAS who were enrolled in parent Study 113. The 113B LCI FAS will be defined as the subset of Study 113B subjects who had LCI data collected in parent Study 113B.

12.2.3 Safety Set

The Safety Set will be defined as all subjects who are enrolled in Study 116 and who received at least 1 dose of TEZ/IVA in Study 116. The Safety Set will be used for all safety analyses, unless otherwise specified.

12.3 Statistical Analysis

The Vertex Biometrics Department or designee will analyze the safety and efficacy data.

The primary objective of this study is long-term safety and tolerability. The secondary objective is long-term efficacy. This section summarizes the statistical analysis of safety and efficacy data. Methodological and related details (e.g., missing data) will be provided in the SAP, which will be finalized before clinical database lock.

The data from Study 116 will be integrated with data from the parent studies for the purpose of safety and efficacy analyses.

The safety analysis period is defined as the **treatment-emergent (TE) Period**. The safety analysis period begins at the first dose of study drug in Study 116 and ends 28 days after the last dose of study drug in Study 116, or at the date of Study 116 participation completion, whichever occurs first. Completion of Study 116 participation will be defined in the SAP.

The safety analyses will be performed on the Safety Set over the Safety Analysis Period, unless otherwise specified.

Safety and tolerability will be assessed by clinical review of all relevant parameters including AEs, PEs, ophthalmologic examinations, clinical laboratory values, vital signs, ECG measurements, and pulse oximetry. Only descriptive summaries will be presented and no statistical testing is planned.

The efficacy analysis period begins at the first dose of study drug in Study 116 and ends at the last study visit at which efficacy data are collected in Study 116. The efficacy analysis will be performed on all subjects in the FAS by parent study for the efficacy analysis period, unless specified otherwise.

Methods of efficacy analyses will be similar for those used in the parent studies. Each of the secondary endpoints (LCI_{2.5}, sweat chloride, CFQ-R, and BMI) will be analyzed using a mixed-effects model for repeated measures (MMRM) with absolute change from baseline during the efficacy analysis period as the dependent variable. The least square (LS) mean and the associated 95% CI at each defined analysis visit will be provided for the corresponding efficacy endpoints.

In addition, descriptive summary statistics will be provided for relevant safety and efficacy parameters.

12.3.1 General Considerations

The precision standards for reporting safety and efficacy variables are provided in an internal Biometrics document that specifies the programming rules including the precision for derived variables.

All individual subject data for subjects who were enrolled in a parent study and who received at least 1 dose of TEZ/IVA in either parent study or in Study 116 will be presented in individual subject data listings.

Continuous variables will be summarized using the following descriptive summary statistics: the number of subjects (n), mean, SD, SE, median, minimum value (min), and maximum value (max).

Categorical variables will be summarized using counts and percentages.

Day 1, unless specified otherwise, will be defined as the day of the first dose of TEZ/IVA, whether the first dose was taken in the parent study or in Study 116.

Baseline value, unless specified otherwise, will be defined as the most recent non-missing measurement (scheduled or unscheduled) collected before the first dose of TEZ/IVA, whether the first dose was taken in the parent study or in Study 116. For ECGs, the baseline value will be defined as the average of the last non-missing pretreatment measurements (scheduled or

unscheduled) before the first dose of TEZ/IVA or the average of measurements (triplicate) before the first dose of TEZ/IVA, whether the first dose was taken in the parent study or in Study 116.

Change (absolute change) from baseline will be calculated as Post-baseline value – Baseline value.

Relative change from baseline will be calculated and expressed in percentage as 100% × (Post-baseline value – Baseline value)/Baseline value.

The data from Study 116 will be integrated with data from the parent studies for the purpose of providing robust safety and efficacy analyses.

Unscheduled visits: Unscheduled visit measurements will be included in analysis as follows:

- In scheduled visit windows per specified visit windowing rules.
- In the derivation of baseline/last on-treatment measurements.
- In the derivation of maximum/minimum on-treatment values and maximum/minimum change from baseline values for safety analyses.
- In individual subject data listings as appropriate.

Visit windowing rules: The analysis visit windows for protocol-defined visits will be provided in the SAP.

Incomplete/missing data will not be imputed, unless specified otherwise.

Outliers: No formal statistical analyses will be performed to detect or remedy the presence of statistical outliers, unless specified otherwise.

Multiplicity: No multiplicity adjustment will be performed.

12.3.2 Background Characteristics

12.3.2.1 Subject Disposition

The number of subjects in the following categories will be summarized overall:

- All Subjects Set
- Safety Set
- FAS

The number and percentage (based on FAS) of subjects in each of the following disposition categories will be summarized overall and by treatment group:

- Completed treatment
- Prematurely discontinued the treatment and the reason for discontinuation
- Completed study (i.e., completed Safety Follow-up Visit)
- Prematurely discontinued the study and the reason for discontinuation

A listing will be provided for subjects who discontinued study drug treatment or who discontinued the study with reasons for discontinuation.

12.3.2.2 Demographics and Baseline Characteristics

Demographics, medical history, and baseline characteristics will be summarized overall based on the FAS.

Demographic data will include the following:

- Age (in years)
- Sex (female and male)
- Ethnicity (Hispanic or Latino, not Hispanic or Latino, and not collected per local regulations)
- Race (White, Black or African American, Asian, American Indian or Alaska Native, Native Hawaiian or Other Pacific Islander, and Other)

Baseline characteristics will include the following:

- Weight (kg)
- Height (cm)
- BMI (kg/m²)
- Geographic region

Disease characteristics will include the following:

- Baseline LCI_{2.5}
- Baseline sweat chloride
- Baseline score of CFQ-R respiratory domain

Medical history will be summarized by MedDRA System Organ Class (SOC) and Preferred Term (PT).

12.3.2.3 Prior and Concomitant Medications

Medications used in this study will be coded by using the World Health Organization Drug Dictionary Enhanced (WHO-DDE) and categorized as the following:

Prior medication: any medication that started before the first dose date of study drug, regardless of when the medication ended.

Concomitant medication: medication continued or newly received on or after the first dose date of study drug through the end of the TE period.

A given medication may be classified as prior, concomitant, or both prior and concomitant.

If a medication has a completely missing or partially missing start/stop date and it cannot be determined whether it was taken before the first dose date or concomitantly, it will be classified as prior and concomitant.

Prior medications and concomitant medications will be summarized descriptively using frequency tables by Preferred Name.

Summaries of medications will be based on the FAS.

Details for imputing missing or partial start and/or stop dates of medication will be provided in the SAP.

12.3.2.4 Study Drug Exposure and Compliance

Duration of study drug exposure (in days) will be calculated as: last dose date – first dose date + 1 day, regardless of study drug interruption.

Exposure summaries will be based on the Safety Set.

Study drug compliance based on the number of tablets taken will be calculated as: $100 \times [(total\ number\ of\ tablets\ dispensed) - (total\ number\ of\ tablets\ returned)] / (total\ number\ of\ tablets\ planned\ to\ be\ taken\ per\ day \times duration\ of\ study\ drug\ exposure\ in\ days)$. The maximum percentage of tablets taken will be 100%.

Study drug compliance based on study drug exposure will be calculated as: $100 \times [1 - (total\ number\ of\ days\ of\ any\ study\ drug\ interruption) / (duration\ of\ study\ drug\ exposure\ in\ days)]$.

Study drug compliance will be summarized descriptively by the n, mean, SD, SE, median, min, and max. They will also be summarized in categories: <80% and $\geq 80\%$ using frequency tables.

Study drug compliance summaries will be based on the FAS.

12.3.3 Efficacy Analysis

All efficacy analyses described in this section will be performed by parent study based on the FAS (115 FAS and 113B FAS), unless specified otherwise. LCI analysis will be based on the 115 FAS and the 113B LCI FAS. The analysis will include all available measurements during the efficacy analysis period.

12.3.3.1 Analysis of Primary Efficacy Variables

Not applicable.

12.3.3.2 Analysis of Secondary Efficacy Variables

Methods of efficacy analyses will be similar for those used in the parent studies. Each of the secondary endpoints (LCI_{2.5}, sweat chloride, BMI, and CFQ-R) will be analyzed using a MMRM, with absolute change from baseline during the efficacy analysis period as the dependent variable. For subjects from Study 115, only those who were randomized to TEZ/IVA treatment group will be included in the MMRM model.

The model will include the absolute change from baseline as the dependent variable; visit as a fixed effect; and subject as a random effect, with or without adjustment for age, genotype mutation group, and baseline value.

In the model, visit will be treated as a class variable, assuming an unstructured covariance matrix to model the within-subject variability. This model imposes no assumptions on the correlational structure and is considered robust. Denominator degrees of freedom for the *F* test for fixed effects will be estimated using the Kenward-Roger approximation. If there is a convergence problem due to the use of an unstructured covariance matrix, a compound symmetry covariance structure will be used to model the within-subject errors. With a mixed-effects model based on a restricted maximum likelihood estimation used for the primary analysis and assuming that, conditional on fixed and random effects, data are missing at random, no imputation of missing data will be performed.

The LS mean and the associated 95% CI at each defined analysis visit will be provided for the corresponding efficacy endpoints.

12.3.4 Safety Analysis

The overall safety profile of study drug will be assessed in terms of the following safety and tolerability endpoints:

- AEs
- Clinical laboratory values (hematology and serum chemistry)
- Standard 12-lead ECGs
- Vital signs
- Pulse oximetry
- PE
- Ophthalmologic examination

Safety endpoints will be analyzed based on the Safety Set using data during the Safety analysis period (TE period). Only descriptive summaries will be presented and no statistical testing is planned.

12.3.4.1 Adverse Events

AEs will be classified as pretreatment AEs or treatment-emergent AEs (TEAEs), defined as follows:

Pretreatment AE: any AE that started before the first dose of study drug

TEAE: any AE that worsened (either in severity or seriousness) or that was newly developed at or after the first dose date of study drug through the end of the TE period.

For AEs with completely missing or partially missing start dates, if there is no clear evidence that the AEs started before or after study treatment, the AEs will be classified as TEAEs.

Details for imputing missing or partial start dates of AEs are described in the SAP.

AE summary tables will be presented for TEAEs only, overall and by treatment group, and will include the following:

- All TEAEs
- TEAEs by strongest relationship
- TEAEs by maximum severity
- TEAEs leading to treatment discontinuation
- Serious TEAEs
- TEAEs leading to death

Summaries will be presented by MedDRA SOC and PT using frequency counts and percentages (i.e., number and percentage of subjects with an event). When summarizing the number and percentage of subjects with an event, subjects with multiple occurrences of the same AE or a continuing AE will be counted once. Only the maximum severity level will be presented in the severity summaries, and the strongest relationship level will be presented in the relationship summaries.

In addition, a listing containing individual subject AE data for TEAEs leading to treatment discontinuation, serious adverse events (SAEs), and deaths will be provided separately. All AEs, including pretreatment AEs, will be presented in an individual subject data listing.

12.3.4.2 Clinical Laboratory Assessments

For treatment-emergent laboratory measurements, the raw values and change-from-baseline values of the continuous hematology and chemistry results will be summarized in SI units by treatment group and visit.

The number and percentage of subjects with at least 1 laboratory event outside threshold criteria for the event during the TE period will be summarized overall and by treatment group, including a shift of the event from baseline to post-baseline. The threshold criteria will be provided in the SAP.

A listing of subjects with elevated LFT results during the TE period will be presented based on any of the following: AST $>3 \times$ ULN, ALT $>3 \times$ ULN, GGT $>3 \times$ ULN, ALP $>3 \times$ ULN, or total bilirubin $>2 \times$ ULN. For each subject in the listing, LFT assessments at all time points will be included (scheduled and unscheduled).

Results of the urine/serum pregnancy test will be listed in individual subject data listings only.

In addition, a listing containing individual subject hematology and chemistry values outside the normal reference ranges will be provided. This listing will include data from both scheduled and unscheduled visits.

12.3.4.3 Electrocardiogram

For treatment-emergent ECG measurements, a summary of raw values and change from baseline values will be provided by treatment group and visit for the following standard 12-lead ECG measurements: RR (msec), HR (beats per minute [bpm]), PR (msec), QRS duration (msec), QRS axis (degrees), QT (msec), and QT corrected for HR intervals (QTcF [msec]).

The number and percentage of subjects with at least 1 ECG event outside of the threshold criteria during the TE period will be summarized overall and by treatment group. The threshold value criteria will be provided in the SAP.

12.3.4.4 Vital Signs

For treatment-emergent vital signs measurements, the raw values and change-from-baseline values will be summarized by treatment group and visit: systolic and diastolic blood pressure (mmHg), body temperature ($^{\circ}$ C), HR (bpm), and respiration rate (breaths per minute).

The number and percentage of subjects with at least 1 event outside the threshold criteria for a vital sign during the TE period will be summarized overall and by treatment group. The threshold value criteria will be provided in the SAP.

12.3.4.5 Physical Examination

PE findings will be presented as an individual-subject data listing only.

12.3.4.6 Other Safety Analysis

Not applicable.

12.3.5 Interim and IDMC Analyses

12.3.5.1 Interim Analysis

IAs may occur at any time during the study. The timing and IA analysis plans will be documented in the SAP. If a parent study is not completely unblinded during an IA, the analysis will be performed according to the relevant unblinding plan. The details of the unblinding process will be provided in the Unblinding Plan.

12.3.5.2 IDMC Analysis

An IDMC will be formed. The IDMC's objectives and operational details will be defined in a separate document (the IDMC charter). The IDMC will conduct regular planned safety reviews of study data as outlined in the IDMC charter.

Details of the IDMC (Section 9.1.4) analysis will be provided in the IDMC Analysis Plan.

13 PROCEDURAL, ETHICAL, REGULATORY, AND ADMINISTRATIVE CONSIDERATIONS

13.1 Adverse Event and Serious Adverse Event Documentation, Severity Grading, and Reporting

13.1.1 Adverse Events

13.1.1.1 Definition of an Adverse Event

An AE is defined as any untoward medical occurrence in a subject during the study; the event does not necessarily have a causal relationship with the treatment. This includes any newly occurring event or worsening of a pre-existing condition (e.g., increase in its severity or frequency) after the ICF is signed.

An AE is considered serious if it meets the definition in Section 13.1.2.1.

13.1.1.2 Clinically Significant Assessments

Study assessments including laboratory tests, ECGs, PEs, and vital signs will be assessed and those deemed to have clinically significant worsening from baseline will be documented as an AE. When possible, a clinical diagnosis for the study assessment will be provided, rather than the abnormal test result alone (e.g., urinary tract infection, anemia). In the absence of a diagnosis, the abnormal study assessment itself will be listed as the AE (e.g., bacteria in urine or decreased hemoglobin).

An abnormal study assessment is considered clinically significant if the subject has 1 or more of the following:

- Concomitant signs or symptoms related to the abnormal study assessment
- Further diagnostic testing or medical/surgical intervention

- A change in the dose of study drug or discontinuation from the study

Repeat testing to determine whether the result is abnormal, in the absence of any of the above criteria, does not necessarily meet clinically significant criteria. The determination of whether the study assessment results are clinically significant will be made by the investigator.

A laboratory value that is Grade 4 will not automatically be an SAE. A Grade 4 laboratory value will be an SAE if the subject's clinical status indicates a life-threatening AE.

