11.4.3 Liver Function Test Parameters

Liver function testing (alanine transaminase [ALT], aspartate transaminase [AST], gamma-glutamyl transferase [GGT], alkaline phosphatase [ALP], direct bilirubin, and total bilirubin) must be performed as noted in [Table 3-1](#) for serum chemistry while subjects are receiving study drug treatment and at the Safety Follow-up Visit. These blood samples should be processed and shipped immediately per the Laboratory Manual.

Subjects with new treatment-emergent ALT or AST elevations of $>3 \times$ upper limit of normal (ULN) and clinical symptoms must be followed closely, including repeat confirmatory testing performed by the central laboratory within 48 to 72 hours of the initial finding and subsequent close monitoring of ALT and AST levels, as clinically indicated. In addition, if ALT or AST is $>5 \times$ ULN, repeat follow-up levels must be obtained within 7 ± 2 days.

If a subject cannot return to the site for confirmatory liver function testing, a local laboratory may be used. Elevations in LFTs at the local laboratory must be reported immediately to the medical monitor, and the subject must have the tests repeated and sent to the central laboratory as soon as possible (ideally within 48 to 72 hours).

Study Drug Interruption:

Study drug administration **must be interrupted** immediately (before confirmatory testing), and the medical monitor must be notified, if any of the following criteria is met:

- ALT or AST $>8 \times$ ULN
- ALT or AST $>5 \times$ ULN for more than 2 weeks
- ALT or AST $>3 \times$ ULN, in association with total bilirubin $>2 \times$ ULN and/or clinical jaundice

A thorough investigation of potential causes should be conducted and the subject should be followed closely for clinical progression.

If no convincing alternative etiology (e.g., acetaminophen use, viral hepatitis, or alcohol ingestion) for the elevated transaminases is identified, regardless of whether ALT or AST levels have improved, study drug treatment must be permanently discontinued if repeat testing within 48 to 72 hours confirms the initial elevation. Subjects in whom treatment is discontinued for elevated transaminases should have their transaminases monitored closely until levels normalize or return to baseline.

Resumption of Study Drug:

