13.1.1.3 Documentation of Adverse Events

All AEs will be collected from the time ICF is signed until the following time points:

- For subjects who do not enroll: until time of withdrawal of consent
- For enrolled subjects who have a Safety Follow-up Visit: through the Safety Follow-up Visit
- For enrolled subjects who do not have a Safety Follow-up Visit, the **earliest** of
 - o 28 days after the last dose of study drug, or
 - o the ETT Visit, if that visit is 3 weeks or later following the last dose of study drug (see Section 9.1.3)
- For enrolled subjects who do not have a Safety Follow-up Visit because they will transition to commercially available CFTR modulator, or if the subject will receive TEZ/IVA through a Vertex-sponsored MAP: through the ETT Visit (Section 9.1.3)

All subjects/caregivers will be queried, using nonleading questions, about the occurrence of AEs at each study visit. When possible, a constellation of signs and/or symptoms will be identified as 1 overall event or diagnosis. All AEs for enrolled subjects will be recorded in the CRF and source document. For subjects who consent, but do not subsequently enroll in the study, AEs will be recorded only in the subject's source documents. The following data will be documented for each AE:

- Description of the event
- Classification of “serious” or “nonserious”
- Date of first occurrence and date of resolution (if applicable)
- Severity
- Causal relationship to study drug(s)
- Action taken
- Outcome
- Concomitant medication or other treatment given

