10.3.1.4 TEAEs of Special Interest

For treatment-emergent elevated transaminase events, respiratory symptoms, and respiratory events (PT lists are provided in

[Appendix H](#)), the following categories will be summarized in terms of frequency counts:

- Subjects with events
- Subjects with events by maximum severity
- Subjects with events leading to treatment discontinuation
- Subjects with events leading to treatment interruption
- Subjects with serious events
- Subjects with related serious events
- Subjects with events leading to death
- Duration of events
- Time-to-onset of first event

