| Weight | 
Weight gain
 
≥5 % increase from baseline ≥10 % increase from baseline ≥20% increase from baseline
 | CTCAE grade 1-3 |

| | |
|------------------------------|-----------------|
| Weight loss | CTCAE grade 1-3 |
| ≥5 % decrease from baseline | |
| ≥10 % decrease from baseline | |
| ≥ 20% decrease from baseline | |

▪ **Appendix H: TEAEs of Special Interest**

Respiratory symptoms are defined as any TEAEs for the following 3 PTs:

- Chest discomfort
- Dyspnoea
- Respiration abnormal

Respiratory events are defined as any of the afore-mentioned respiratory symptoms, or any TEAEs for the following 4 additional PTs:

- Asthma
- Bronchial hyperreactivity
- Bronchospasm
- Wheezing

The following AE preferred terms will be selected for elevated transaminase:

- Alanine aminotransferase abnormal
- Alanine aminotransferase increased
- Aspartate aminotransferase abnormal
- Aspartate aminotransferase increased
- Transaminases abnormal
- Transaminases increased
- Liver function test abnormal
- Liver function test increased
- Hypertransaminasaemia
- Hepatic enzyme abnormal
- Hepatic enzyme increased

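### A transaminase elevation recorded only under a liver diagnosis matches no term in the SAP's elevated-transaminase list, so the special-interest summary may undercount such events (minor)

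*Protocol*

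**What the plan says.** **How events are named.** Protocol 13.1.1.2 covers abnormal laboratory and other assessments that become adverse events. Its preference is "When possible, a clinical diagnosis for the study assessment will be provided, rather than the abnormal test result alone". The fallback is: "In the absence of a diagnosis, the abnormal study assessment itself will be listed as the AE". Protocol 13.1.1.3 points the same way for clinical presentations: "When possible, a constellation of signs and/or symptoms will be identified as 1 overall event or diagnosis".

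**How events are selected for the summary.** SAP 10.3.1.4 sets out a dedicated summary "For treatment-emergent elevated transaminase events, respiratory symptoms, and respiratory events". Its rows are subjects with events, maximum severity, discontinuation, interruption, serious, related serious, death, duration, and time to first onset. Membership is decided by preferred term. Appendix H introduces the liver list with "The following AE preferred terms will be selected for elevated transaminase" and gives 11 terms.

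**What happens after a marked elevation.** Protocol 11.4.3 sets enzyme and bilirubin criteria for interrupting study drug before confirmatory testing. It then says: "A thorough investigation of potential causes should be conducted and the subject should be followed closely for clinical progression". Viral hepatitis is among the alternative causes it gives as examples.

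**The concern.** The two documents use different handles on the same event. The protocol moves the recorded term away from the test result whenever a diagnosis is available. The SAP finds events of special interest through test-result terms. An event recorded exactly as the protocol prefers can therefore fall outside the list meant to collect it.

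Long-term safety is the primary objective, and elevated transaminases are one of only three special-interest groups in the SAP. The 10.3.1.4 summary is the one place where liver-related AE terms are pooled, and the only AE summary that specifies duration and time to onset. If some events are missing, its counts are too low, and its severity, duration and onset figures describe only the events that kept a test-result term.

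**Working it through.** The plan gives no figure to reproduce here. The check is a count of terms and a comparison of sections.

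**1. Count the Appendix H liver terms.**
- Five tests or analytes (ALT, AST, transaminases, liver function test, hepatic enzyme), each listed as abnormal and as increased: 5 × 2 = 10.
- One condition term: "Hypertransaminasaemia".
- Total: 10 + 1 = 11. Test-result terms: 10/11 = 90.9%. Terms naming a specific liver diagnosis (hepatitis, liver injury, jaundice, hepatic failure and the like): 0/11.

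**2. Trace one event through both documents.** Suppose a child's ALT meets an interruption criterion in Protocol 11.4.3 and viral hepatitis is then found.
- Under Protocol 13.1.1.2, further diagnostic work-up or a change in study drug makes the result clinically significant, so it is an AE.
- A diagnosis exists, so the preferred term to record is the diagnosis.
- No hepatitis term is in Appendix H. If the diagnosis is the only term recorded, the child enters no row of 10.3.1.4, including the interruption row, although the drug was interrupted for raised transaminases.

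**3. See which rows are most exposed.**
- *Interruption.* Protocol 11.4.3 requires interruption before the cause is known, so this row should include children who later receive a diagnosis. It is the clearest gap.
- *Discontinuation.* The same section makes discontinuation mandatory when the elevation is confirmed and no persuasive other cause is found. Such events will often have no diagnosis, keep a test-result term, and be selected. Exceptions are possible, such as a recurrence soon after rechallenge or an investigator who records drug-induced liver injury. This row is less clearly exposed.
- *Pooled severity, duration, time to onset.* A missed event is missing here too, and no other AE table gives these for liver events as a group.

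**4. Find where the same child still appears.**

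| Output | Captures the diagnosed event? | What it lacks |
|---|---|---|
| SAP 10.3.1.2 tables by SOC and PT (severity, serious, discontinuation, interruption, death) | Yes, under its own PT | Liver terms not pooled; no duration or onset |
| SAP 10.3.1.1 listings (discontinuation, interruption, SAEs, deaths) | Yes, where applicable | Individual records only |
| SAP 10.3.2 LFT listing (for example ALT or AST >3xULN) | Yes, whatever the AE term | No AE attributes |
| SAP Appendix G threshold tables | Yes, if measured centrally | No AE attributes; local results excluded by 10.3.2 |

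The central-only rule matters somewhat. Local laboratories are allowed for urgent issues (Protocol 11.4.2), for confirmatory liver tests (11.4.3), and for some subjects under the COVID-19 addendum.

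**5. Scale.** The documents give no event rate and no share recorded by diagnosis, so the undercount cannot be computed. Only the weight of one subject can be stated. About 121 subjects (56 + 65) are potentially eligible, so one missed subject is 1/121 = 0.8 percentage points, or slightly more if the Safety Set is smaller.

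**The case against.** The strongest reply is that little is lost. The general TEAE tables already report severity, seriousness, interruption, discontinuation and death by preferred term, and the laboratory outputs do not depend on AE coding at all. That is correct, and it is why the point is minor. A reader might infer that 10.3.1.4 is the only AE output with these attributes for liver events. The SAP does not support that: 10.3.1.2 and the 10.3.1.1 listings supply most of them event by event. What 10.3.1.4 alone provides is the pooled view, plus duration and time to onset.

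A second reply is that the group is labelled elevated transaminase, not hepatic disorders, so a narrow list fits its name. This has some force for liver diagnoses without raised enzymes. It does not cover a child whose transaminases did rise and whose event was then given a diagnosis. That child is within the label and outside the list.

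A third reply is that the recording rule is conditional. It applies where a diagnosis is possible, and it speaks of the test result *alone*, so a site may record both terms. Some causes, such as acetaminophen use, need not turn an ALT term into a liver diagnosis. This also stands, so the summary may miss events rather than must.

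**Conclusion.** The mismatch is real and follows from the text: 0 of 11 listed terms would select a transaminase elevation recorded only as a liver diagnosis. The special-interest summary may therefore undercount such events, most plainly in the interruption row and in the pooled severity, duration and onset rows. This assumes that at least some sites follow the diagnosis preference and do not also record a test-result term.

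It is tempting to go further and say that the lost events are the worst ones, so that the hepatic profile will look milder than it was. The documents do not support this. They say nothing on severity by type of term. Protocol 11.4.3 attaches mandatory discontinuation to confirmed elevations without another cause, and those are the ones likely to keep a listed term. Nor is there a basis for any stated fraction of a row being lost.

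Severity: minor. The summaries are descriptive, the events are visible elsewhere, and the defect is easily repaired.

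**What to change.** Amend SAP Appendix H and 10.3.1.4 before the Part A database lock:

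1. Keep the present 11 terms unchanged as the narrow definition.
2. Add a prespecified broad definition: those 11 terms plus a fixed list of hepatic diagnosis terms, for example hepatitis (including viral), liver injury, drug-induced liver injury, hepatotoxicity, jaundice and hepatic failure. Appendix H already has this two-tier form for the lung, where three respiratory-symptom terms are extended by four more to define respiratory events.
3. Report both tiers side by side for every row of 10.3.1.4.
4. Cross-tabulate subjects with an AE in each tier against subjects with ALT or AST >3xULN in the TE period, a cut-off the SAP already uses for its LFT listing. State whether local results are included in the cross-tabulation.

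The cost is a short SAP amendment, one extra set of columns and one small table, all from data already collected and coded. The downside is that the broad tier will include some events with a non-drug cause. Showing the narrow tier beside it, with the individual listings, lets the reader see which these are.
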